5.2. Hypothesis to be accepted or rejected on the basis of statistical data from the clinical trial.

The OPTIFILL clinical trial is a non-inferiority trial; the aim is to show that the 2-year efficacy rates for the 2 filling materials PA1704 and BioRoot™ RCS are comparable.

i.e.:

 π_N = 2-year efficacy rate of PA1704 based on soft radiological and clinical criteria,

π_R = 2-year efficacy rate of BioRoot™ RCS based on soft radiological and clinical criteria,

 $\Delta = \pi_N - \pi_R$, the difference in efficacy at 2 years between the 2 treatments,

 Δ_L = limit corresponding to a clinically insignificant difference (i.e. the greatest difference in tolerated efficacy between the 2 products) (see Chapter 7.2 for details).

The hypotheses are:

H0: $\Delta \le -\Delta_L$, PA1704 is inferior to BioRoot[™] RCS

H1: $\Delta > -\Delta_L$, non-inferiority of PA1704 compared to BioRoot[™] RCS

Using Dunnett and Gent's χ^2 test (Dunnett CW and Gent M. 1977; Elie C. et al., 2008), we will reject H0 and conclude that the new PA1704 material is not inferior to the BioRootTM RCS reference material if the difference in efficacy between the 2 products is greater than the non-inferiority limit (see Figure 3).

[figure not shown]

Figure 3: Non-inferiority trial and associated hypotheses (according to Elie et al., 2008).

5.3. Claims and expected performance of the device under investigation that need to be verified.

- Permanent filling of the root canals of permanent and mature teeth.
- Preservation of tooth function.

5.4. Risks and undesirable effects expected from the device, which must be assessed.

The adverse effects of the device are not known in the patient and will be investigated, in particular the occurrence of any allergic reaction, as soon as the material is applied to the root canals.

6. Clinical trial design

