6.6.5. Data quality & monitoring

Data monitoring will be carried out by the CRO's CRAs, in accordance with Good Clinical Practice aimed at guaranteeing the quality of the trial. As the OPTIFILL trial is a category 1 RIPH involving a class IIa medical device that is not CE marked, the level of control will be high.

The CRAs will carry out regular remote monitoring *via* the ENNOV Clinical software application to track recruitment and check the integrity of the data entered into the eCRF. Requests for corrections or clarification of data will be sent to the investigator electronically.

In addition, the CRO's CRAs will regularly visit the investigating centres; 6 site visits are planned: 1 visit soon after the first enrolments, then a site visit after each follow-up visit provided for in the protocol, for up to 5 years of patient follow-up. The CRAs will check and verify consent forms, the consistency of critical data (PEC clinical criteria, AEs, patient record data, device defects) and equipment.

Visits will be organized after making an appointment with the investigator. The CRA must be able to consult:

- Consent forms,
- Observation and monitoring records,
- Patient source files (paper and/or electronic format),
- Medical devices made available (PA1704 and Bioroot™ RCS)
- Investigator file provided by the CRO.

7. Statistical considerations

7.1. Software used:

 Creation of the input template for the electronic CRF and patient record, database media: Ennov Clinical version 8.0,

Statistical analysis: JMP[®] version 15.0.0 or later (SAS Institute) on Windows 10 Pro.

7.2. Size of sample:

Based on the assumption that there is no difference in efficacy at 2 years between the 2 filling materials (PA1704 and BioRoot™ RCS) and that the expected efficacy rate of BioRoot™ RCS after initial and repeated endodontic treatment is 90% (Zavattini et al., 2019; Chybowski et al., 2018, Bardini et al., 2016), we calculate that a minimum of 66 subjects per group must be enrolled **to show non-inferiority of PA1704 over BioRoot™ RCS** with a confidence interval of 80%, a unilateral alpha risk of 5% and a 13% difference in efficacy tolerance between the 2 products (Ng 2007; Ng 2008; Eyuboglu 2016). By enrolling an additional 20% of patients in order to take into account those lost to or withdrawn from the trial, **the number of patients who must be included is 80 in each group, or 160 patients in total.**

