7.3. Degree of significance and power of the clinical trial

The main analysis will be carried out using a one-tailed statistical test with a significance threshold α set at 5%. The clinical trial is designed to ensure 80% power for the main analysis test. Secondary analyses will be carried out using two-tailed statistical tests with a significance threshold α set at 5%.

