7.7. Statistical methods

The statistical methods are based on the following elements and will be detailed in the Statistical Analysis Plan.

7.7.1. Sample description:

The description of the subjects enrolled who completed the trial and those enrolled who left prematurely will be presented using a table of absolute (N) and relative (%) frequency. Reasons for premature discharge and deviations from the protocol will be listed.

7.7.2. Descriptive analyses:

Clinical data collected at enrolment and at each visit will be described. Descriptive statistics will be presented according to the nature of the criterion analyzed:

- Quantitative variable: sample size, number of missing data sets, mean, standard deviation, median, minimum and maximum;
- Qualitative variable: absolute frequencies (N) and relative frequencies (%) per class in each group, number of missing data.

Graphs will be provided for each variable.

7.7.3. Comparative analyses:

A comparison of 2 independent means will be made using the Student's t-test; if the variances are unequal (verified by the Fisher's test), use the Welch's test instead of the Student's test. If the conditions for applying the Student test are not met (n < 30), the non-parametric Wilcoxon test is used.

2 independent percentages are compared using Pearson's Chi-2 test. If the conditions for application are not met (at least one theoretical number < 5), Fisher's exact test is used.

7.7.4. Analysis of primary performance criterion:

As a reminder, the primary performance criterion is the efficacy rate at 24 months of treatment based on clinical criteria assessed by the investigator (tooth functionality and pain level) AND radiological criteria assessed blind by independent reviewers (complete healing, reduction of lesions, failure). In the event of failure at 6 or 12 months, the patient will be considered to have failed at 24 months.

The primary criterion will be analyzed using 2 approaches, in accordance with the literature:

- **Primary analysis of soft criteria**: treatment rates with complete or incomplete cure are compared against failure rates;
- **Secondary analysis of strict criteria**: treatment rates with complete healing are compared against rates of failure or incomplete healing (complete healing can take up to 4 or 5 years).

The comparison of efficacy rates between the 2 groups will be carried out using the Dunnett and Gent χ^2 test (Dunnett CW and Gent M 1977; Elie C et al 2008).

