In addition, the difference in the 2-year efficacy rate between the 2 materials are to be calculated; its unilateral confidence interval of 95% will be provided and the lower limit is will be compared against the non-inferiority limit.

The main performance analysis will be carried out on the PP population, in accordance with the recommendations for non-inferiority studies. This will be complemented by an analysis of the mITT population to check the stability of the results.

7.7.5. Analysis of secondary performance criteria:

Efficacy rate at 6 months based on radiological and clinical criteria: Description and comparison, between the PA1704 arm and the BioRoot™ RCS arm, of the 6-month efficacy rate by Pearson's Chi-2 test or Fisher's exact test.

Efficacy rate at 12 months based on radiological and clinical criteria: Description and comparison, between the PA1704 arm and the BioRoot™ RCS arm, of the 12-month efficacy rate by Pearson's Chi-2 test or Fisher's exact test.

Quality of apical obturation at T0 (complete obturation, under-filling or over-filling): Description and comparison, between the PA1704 arm and the BioRoot™ RCS arm, of the proportions of apical obturation quality by Pearson's Chi-2 test or Fisher's exact test.

Density of root canal filling at T0, 6 months, 12 months, 24 months: Description and comparison at each time point, between the PA1704 arm and the BioRoot™ RCS arm, of the proportions of canals with an

obturation density deemed sufficient and the proportions of canals free of voids, by Pearson's Chi-2 tests or Fisher's exact tests.

Progress of material resorption over 24 months, in the event of over-filling at T0 (6 months, 12 months and 24 months): Description and comparison, between the PA1704 arm and the BioRoot™ RCS arm, of the proportions of patients with resorbed materials among patients who were over-filled at T0 by Pearson's Chi-2 test or Fisher's exact test.

Pre-operative and post-operative pain experienced by the patient (VAS 0-100 mm) at T0 (end of surgery), 12h, 24h, 48h, 72h and 7 days: For each time point, description and comparison of the pain, between the PA1704 arm and the BioRoot™ RCS arm, by a Student, Welch or Wilcoxon test. A figure representing average pain as a function of assessment times per arm will be provided. The causes of the pain will be described.

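### The primary non-inferiority test is named without its formula, interval method or decision rule; run as an uncorrected chi-square, its one-sided error is about 8%, not 5%

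*Combined protocol and SAP*

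**What the plan says.** Section 7.3 sets the error rate: "The main analysis will be carried out using a one-tailed statistical test with a significance threshold" of 5%. It adds: "The clinical trial is designed to ensure 80% power for the main analysis test". Section 7.2 takes a 90% efficacy rate in both arms, with "a unilateral alpha risk of 5% and a 13% difference in efficacy tolerance between the 2 products", and arrives at 66 per group, raised to 80 for losses.

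Section 5.2 writes the null hypothesis, labelled "PA1704 is inferior to BioRoot" RCS, as a difference at or below minus the margin. It makes the Dunnett-Gent chi-square the means of rejecting that null. Section 7.7.4 repeats the choice: "The comparison of efficacy rates between the 2 groups will be carried out using the Dunnett and Gent" chi-square. The synopsis does the same. The test is identified by citation alone in all three places.

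The synopsis and 7.7.4 then add the difference in 2-year rates: "its unilateral confidence interval of 95% will be provided", with its lower limit compared with the margin. The interval method is not named. Nothing says whether both results must be favourable or which prevails. The main analysis is on the per-protocol set. Section 7.7 defers detail to a Statistical Analysis Plan, which 7.7.9 says will be written before the first interim analysis.

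**The concern.** A chi-square for a shifted null can be computed in several ways, and at this sample size they do not share one error rate. In the plainest form, expected counts keep the observed total of successes and put the two rates exactly 13 points apart, and the four-cell sum is referred to chi-square on one degree of freedom. That form divides by too small a variance when the two null rates differ, as they do at 90% and 77%, so it rejects too often.

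At stake is the false non-inferiority rate of the trial's one confirmatory comparison, in a first-in-human study before CE marking. A sealer that is truly 13 points worse could pass more often than the stated 1 time in 20. A second consequence is practical: the test and the reported limit can contradict each other, and the plan has no rule for that case.

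**Working it through.** **Inputs.** One-sided alpha 5% and power 80% (7.3); 90% in both arms and margin 13 points (7.2), so the null boundary is 90% versus 77%; 1:1 allocation (6.1); 66 evaluable and 80 enrolled per arm (7.2). The formulas for forms (a) to (c) are assumptions, because the cited paper is not part of the documents.

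**Step 1: the plan's own figure.** With the unpooled variance, n = (1.645 + 0.842)² × 2 × 0.90 × 0.10 / 0.13² = 65.9, hence 66 per arm. Then 66 × 1.20 = 79.2, rounded to 80. Both planned figures reproduce.

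**Step 2: forms of the test.** Let xN and xR be the successes for PA1704 and BioRoot RCS, with n per arm. The null rates are pR = (xN + xR + 0.13n)/(2n) and pN = pR - 0.13. Write vR = pR(1 - pR) and vN = pN(1 - pN).

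- (a) Sum of (O - E)²/E over four cells, uncorrected; signed root compared with 1.645.
- (b) The same with a 0.5 continuity correction.
- (c) z = (observed difference + 0.13)/√((vN + vR)/n).
- (d) Wald lower 95% limit above -13 points.
- (e) Farrington-Manning score test (restricted maximum likelihood).

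**Step 3: exact enumeration.** Size is the sum of Bin(xN; n, 0.77) × Bin(xR; n, 0.90) over all tables that pass. Power uses 0.90 in both arms.

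| Rule | Size, n = 66 | Size, n = 80 | Power, n = 66 |
|---|---|---|---|
| (a) uncorrected chi-square | 8.0% | 7.2% | 80.4% |
| (b) with 0.5 correction | 4.8% | 4.7% | 74.6% |
| (c) z-form | 5.8% | 5.5% | 81.8% |
| (d) Wald limit alone | 5.6% | 5.5% | 79.9% |
| (a) and (d) both required | 5.5% | 5.5% | 72.2% |
| (e) score test | 5.0% | 5.0% | 77.0% |

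The score test has 84.3% power with 80 per arm.

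The size also moves with the true comparator rate (66 per arm):

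| Rule | 85% | 90% | 92% | 95% |
|---|---|---|---|---|
| (a) | 6.5% | 8.0% | 9.1% | 11.6% |
| (b) | 3.9% | 4.8% | 5.6% | 7.2% |
| (e) | 5.1% | 5.0% | 4.9% | 4.7% |

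For (a), (b) and the joint rule, tables whose expected BioRoot RCS rate reaches 100% were counted as not passing. They carry only 0.02% probability at 90% versus 77% but about 8% at 90% in both arms (n = 66). The sizes at 90% are therefore unaffected, whereas the powers of those three rules depend on the convention.

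**Step 4: why (a) runs high.** The four-cell sum is equivalent to dividing the shifted difference by a variance built on the harmonic mean of vN and vR, where the arithmetic mean is the right one. The ratio is (vN + vR)²/(4 vN vR). With vR = 0.0900 and vN = 0.1771 this is 0.2671²/(4 × 0.0900 × 0.1771) = 0.0713/0.0638 = 1.12. The effective critical value is 1.645/√1.12 = 1.555, a one-sided error of about 6.0% even in large samples. The rest, up to 8.0%, is small-sample error.

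**Step 5: an example of conflict.** Take BioRoot RCS 60/66 and PA1704 57/66.

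- pR = (117 + 8.58)/132 = 0.9514 and pN = 0.8214. The expected PA1704 successes are 54.21, so O - E = 2.79.
- (a): 2.79² × (1/54.21 + 1/11.79 + 1/62.79 + 1/3.21) = 3.35, so z = 1.83 and p = 0.034: passes.
- (b) z = 1.50, (c) z = 1.56, (e) z = 1.46 (p = 0.072): none passes.
- (d): -0.0455 - 1.645 × √((57 × 9 + 60 × 6)/66³) = -0.0455 - 0.0906 = -13.6 points: fails.

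**Step 6: how often (a) passes while (d) fails, n = 66.** At 90% in both arms, 80.4% - 72.2%, about 8% of trials. At 90% versus 77%, 8.0% - 5.5% = 2.5%.

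**The case against.** A reader might infer that the Dunnett-Gent test as such breaches the stated 5%. The documents do not support that. They give no formula, so the 8% belongs to one reading. With a 0.5 correction the size at the plan's own 90% rate is 4.8%, and the z-form exceeds 5% by less than one point. In the example above, only the uncorrected form passes. This stands, and it is why the point is conditional.

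The plan also reports a lower limit. If that had to pass too, and were Wald, even the uncorrected chi-square would have size 5.5%. This stands as arithmetic, but the plan does not state that rule: 5.2 lets the chi-square reject the null, and 7.7.4 introduces the limit as an addition.

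Section 7.7.3 treats a chi-square as unsuitable when an expected count is below 5. Such tables supply 4.2 of the 8.0 points. However, that rule is written for Pearson's test, its fallback (Fisher's exact test) does not test a 13-point shift, and the remaining 3.9 points come from tables that meet the condition.

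Finally, the detail is deferred to a later Statistical Analysis Plan. That makes the gap easy to close, but it leaves the error rate unsettled now. Nor does the corrected form settle it: its size is 5.6% at a 92% comparator rate and 7.2% at 95%. Section 3.1.3 itself cites a BioRoot RCS result of 90% with a 95% interval of 80 to 96%.

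**Conclusion.** The primary analysis is under-specified in four respects: the statistic, the continuity correction, the interval method, and the precedence between test and limit. At the plan's 90% rate and 66 per arm, the stated one-sided 5% becomes anything from 4.8% to 8.0%, depending on how the gaps are filled. The upper figure (7.2% with 80 per arm) rests on the uncorrected four-cell form, which fits the wording but remains an assumption. The Wald figures likewise assume a method that the plan does not name.

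The documents therefore support a specification gap in which one natural reading inflates the error. They do not support a finding that the trial's test is invalid. It should be corrected before the analysis plan is final, but it ranks below a defect that must block the trial, because the excess depends on the form assumed.

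**What to change.** In 5.2, 7.7.4 and the synopsis, replace the Dunnett-Gent chi-square with the Farrington-Manning score test at one-sided 5%. Report the score-type lower 95% limit obtained by inverting the same test, and make it the single decision rule: non-inferiority is concluded only if that limit lies above -13 points. Test and limit then always agree, and the size stays between 4.7% and 5.1% over comparator rates of 85% to 95% with 66 per arm.

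In 7.3, state the exact power of this rule at 90% in both arms: about 77% with 66 evaluable per arm and 84% with 80. The cost is wording, a few lines of code and a less favourable stated power at 66.

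If the sponsor prefers to keep Dunnett-Gent, the plan must give the formula, the continuity correction, the treatment of tables whose expected rate reaches 100%, the interval method and which result decides, together with the resulting size and power.

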Measurement time and people in charge of evaluation:

For each criterion, this information is given in the table above.

Generally speaking, the assessment of performance and safety criteria begins with the root canal obturation.

Method of evaluating the efficacy rate of initial or repeat endodontic treatment (at 6 months, 12 months and 24 months for the 2 arms; and 3.5 years and 5 years for the PA1704 arm):

Therapeutic efficacy is a composite criterion based on the radiological data assessed **in blind conditions** by reviewers AND on the clinical data assessed **in an open-label manner** by the investigator at the follow-up visits at 6 months, 12 months, 24 months, 3.5 years and 5 years (only the PA1704 arm for the last 2 visits). With regard to the blind evaluation of the radiological criteria by two independent reviewers, the following clarifications are provided:

- The reviewers shall examine the anonymized retro-alveolar images (JPEG files as described in the imaging procedure in section "Equipment to be used to evaluate clinical trial variables and arrangements for monitoring maintenance and calibration." of this chapter) and answer the following questions:
 - Apical lesion: 1) Presence, absence or appearance of a lesion compared with the TO reference image? 2) In the case of a pre-existing lesion at TO, what is the evolution of the size of the lesion (reduction, stabilization or increase)?
 - Root canal filling density: 1) Is the radiopacity sufficient? 2) Presence of at least one bubble in the filling material?
 - Resorption of extruded material where applicable: Is the extruded material still present in the apical space?
- Timetable: 5 centralized image review campaigns are planned, one before each statistical analysis:
 - o 1st review campaign: At the end of the 6-month follow-up of all enrolled patients, a blind review of the T0 reference image and the 6-month follow-up image,
 - o ^{2nd} campaign: after 12 months' clinical follow-up of all patients, blind review of the 12-month check-up image,
 - o 3rd campaign: After 24 months of clinical follow-up for all patients, a blind review of the 24-month check-up image,
 - 4th campaign: After approximately 3.5 years of clinical follow-up of the patients treated with the PA1704 MD, a centre-blind review of the 3.5-year follow-up image,

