Retro-alveolar X-rays are taken with an angulator using the parallel planes technique; the **entire tooth should be visible in the image** (crown to apex, passing through the root). There are no other specific settings imposed for the devices.

The images will be converted to .jpg format, without filters, and anonymized before being uploaded to the eCRF.

✓ Procedures for replacing subjects, if necessary.

See Chapter 7.4

6.2. Medical devices under investigation (ready-to-use material PA1704) and comparator (BioRoot™ RCS powder-liquid material)

✓ Comparator Medical Device Description — BioRoot™ RCS:

The selected comparator MD was the BioRoot™ RCS permanent root canal filling material.

BioRoot™ RCS is a Class III implantable medical device for dental use manufactured by Septodont. BioRoot™ RCS is based on Active Biosilicate Technology (ABS). It is a mineral root canal cement composed mainly of tricalcium silicate, zirconium oxide and calcium chloride. It comes in the form of **two products (powder-liquid) that are to be mixed**. Clinical indications, contraindications, characteristics, instructions for use, warnings, storage and disposal procedures are detailed in the instructions for use (see Annexe 3).

Thus, the medical device under investigation (PA1704) and comparator device (BioRoot™ RCS) are 2 calcium silicate-based cements, which are used for the same endodontic indications but come in 2 different forms, as a powder-liquid mixture or as a ready-to-inject paste. The 2 medical devices are similar and the aim of this study is to show that the performance and safety of the new material are not affected by the change in presentation.

✓ Exposure to medical devices under investigation and comparator

Patients included in the study will randomly receive one of 2 filling materials, PA1704 or BioRoot™ RCS, to treat one tooth (one or more root canals depending on the type of tooth affected by pulpal disease). The medical device is administered (implanted) only once, on the day of the endodontic treatment. The material is implanted for the long term, as it is intended to seal the root canals permanently. It is not intended to be removed during the trial, nor after the end of the trial, except where the treatment has failed with an indication to restart treatment.

✓ List of any other medical devices or medicines to be used during the clinical investigation.

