Initial or repeated endodontic treatment is a surgical procedure that involves several stages and requires the use of several surgical instruments, solutions and filling materials. Several endodontic techniques exist for the preparation and filling of a root canal; these are authorized for trial purposes and practitioners shall maintain their usual practice.

The medical devices and medicines used are:

- Instruments available for shaping the canal: all types of file or broach, manual or mechanical (continuous or alternating rotation system, with or without apex locator).
- Irrigation solutions used to clean the canal:
 - Disinfectant solutions: sodium hypochlorite (NaOCI, mandatory), Chlorhexidine (not systematic),
 - Chelating rinse solutions: EDTA, HEDP, citric acid or other solutions. Solution activation techniques may vary (sonic system, ultrasound, Erbium Yag laser, other laser, other).
- A neutral, semi-solid, compactable filling material to be combined with the luting cement: a master cone of gutta-percha (single cone technique) or several cones of gutta-percha (cold lateral condensation technique).
- Watertight coronal reconstruction material: glass ionomer cement or bonded composite (the use of a temporary cement such as Cavit® is strongly discouraged and the use of IRM® cement is not authorized within the framework of this trial).

✓ Number of devices under investigation to be used and their justification.

A total of 80 patients will receive PA1704 (single dose, amount required for a monoradiculated or multiradiculated tooth) and 80 patients will receive BioRoot™ RCS (single dose, amount required for a monoradiculated or multiradiculated tooth).

Number of PA1704 MD to be used: 1 syringe of 0.5 g of cement can seal up to 5 canals. One syringe will be used for a single patient. **80 syringes will have to be used**.

Number of Bioroot™ RCS MD to be used: bearing in mind that one kit can seal 35 canals (i.e. 1 kit used for several patients) and that a vial of powder can be kept for 6 months after opening, 2 BioRoot™ RCS kits will be needed in each investigating center to cover the 9-month recruitment period.

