6.5.2. Visit procedure

Each patient enrolled in the study will be followed-up with for 2 years or 5 years, depending on the randomized group:

- Arm of the comparator medical device BioRoot™ RCS: Once the endodontic treatment has been completed and the permanent coronal restoration has been carried out,3 follow-up visits are scheduled: A visit at 6 months,12 months, and 24 months.
- Arm of the investigational medical device PA1704: Once the endodontic treatment has been completed and permanent coronal restoration has been carried out, there will be 5 follow-up visits: A visit at 6 months, 12 months and 24 months; at the end of the 24-month follow-up period, patients will be offered 2 further visits: One in the 4th year after the endodontic treatment (approx. 3.5 years ± 6 months) and one visit in the 5th year after the endodontic treatment (approx. 5 years ± 6 months).

For each patient and at each visit, a clinical examination and a retro-alveolar X-ray will be performed to assess the results of the treatment. The procedure for taking the images is described in Section "Equipment to be used to evaluate clinical trial variables and arrangements for monitoring maintenance and calibration." of Chapter 6.1.

The procedure for the visits is as follows (see the diagram in section Table 7):

V0 — Selection visit:

— diagnosis (including a preoperative 2D retroalveolar X-ray; the entire tooth — from the *crown to the root to the apex* — must be visible in the image; the image must be uploaded to the eCRF after the patient has been included; no blind review of this image),

- verification of eligibility,
- information about the trial and handover of consent form,

Patients will be included after diagnosis of the need for endodontic treatment.

V1 — Enrolment visit (T0)

- Collection of written consent
- Recording of patient characteristics at enrolment:
 - Sex, age, history and treatment at enrolment, smoking status,
 - Oral-dental health: DMFT index and CPITN index (record each value and then the CPITN index will be calculated automatically in the eCRF),
 - Characteristics of the tooth to be treated: tooth number, number of canals to be filled, indication for initial or repeat endodontic treatment, pulp diagnosis (irreversible pulpitis, necrotic pulp, living pulp with indication for ET) and periapical diagnosis (presence of an apical lesion, symptomatic tooth), preoperative pain (see pain record in the patient record detailed in the paragraph below).

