6.6. Monitoring plan and data management

6.6.1. Data Collection

For each patient, the data collected during the trial will be spread over 3 media:

- an electronic case report form (eCRF) for the investigator,
- a follow-up booklet to be completed by the patient,
- a database dedicated to blind X-ray review campaigns.

All the information required by the protocol must be provided on these media. They must include the data needed to confirm compliance with the protocol and all the data required for statistical analysis, and enable major deviations from the protocol to be identified.

The people responsible for filling in the CRFs must be defined and identified in the center's task delegation table and recorded in the trial's files at each investigating center. They undertake to comply with the rules for completion set out in the specific manual handed out during the set-up visit.

In this trial, no directly identifying information (identity, address, social security number) or sensitive information will be collected.

The health data collected concerns only:

- patient demographics (gender, age),
- relevant history and treatments taken at the time of enrolment,
- data relating to the tooth to be treated: tooth number, pulpal and periapical pathology, number of canals to be treated,
- pre— and post-operative X-ray image(s); these will all be anonymous, distinguishable by the subject's identifier number.

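### Filling density and voids are to be compared canal by canal with tests for independent observations, although patients are randomised and one tooth can supply several canals; the recorded unit is itself unclear

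*Combined protocol and SAP*

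**What the plan says.** Section 7.7.5 takes the canal as the unit for density. At each of four time points (T0, 6, 12 and 24 months) it compares two proportions of canals, those with "obturation density deemed sufficient and the proportions of canals free of voids", by Pearson's or Fisher's test. Section 7.7.3 gives these tests for comparing two independent percentages. Section 7.3 sets the level: "Secondary analyses will be carried out using two-tailed statistical tests with a significance threshold α set at 5"%.

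Randomisation is by patient, 1:1 (section 6.1). Section 6.2 says each patient receives one of the two materials "to treat one tooth (one or more root canals depending on the type of tooth affected by pulpal disease"), and that "1 syringe of 0.5 g of cement can seal up to 5 canals. One syringe will be used for a single patient". Section 6.5.2 records at V1 the "tooth number, number of canals to be filled, indication for initial or repeat endodontic treatment".

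The plan is less clear on how density is read. In section 6.1 the blinded X-ray readers are asked "Is the radiopacity sufficient? 2) Presence of at least one bubble in the filling material"; no canal is mentioned. In the V1 list of section 6.5.2, the level of obturation is to be evaluated for each canal, but the next item, density, carries no such words. The V3 to V5 items in the same section also name no canal unit for density. Readings go into "a database dedicated to blind X-ray review campaigns" (section 6.6.1), whose layout is not in the documents.

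The neighbouring resorption criterion in 7.7.5 is worded as a proportion of patients, so the canal unit is specific to density and voids.

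**The concern.** Canals of one tooth share the patient, the operator, the session's material and the X-ray image, so their readings are likely to be alike. A test that counts each canal as a separate observation then credits the data with more information than they hold, and it can find differences between the arms too often.

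The quality of the filling, including density, is a stated secondary objective, and section 3.1.3 presents the ready-to-use syringe form as less prone to heterogeneity in preparation. Density and voids are therefore natural places to look for a difference between the two presentations. A false finding could go either way, as a spurious advantage or a spurious deficit for PA1704. The first such results arrive with the 6-month interim analysis of secondary criteria.

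**Working it through.** **The plan's own figure.** Section 7.2 assumes 90% efficacy in both arms, a 13-point margin, one-sided 5% and 80% power:

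n = (1.645 + 0.842)² × 2 × 0.90 × 0.10 / 0.13² = 65.85, so 66 per arm, as stated. Then 66 × 1.2 = 79.2, so 80 enrolled per arm, as stated.

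This calculation counts one result per patient and is not touched by the present point. It supplies the two sample sizes used below.

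**Inputs from the documents:** patient-level 1:1 allocation; 66 or 80 patients per arm; one tooth per patient with one or more canals; two-sided 5%.

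**Inputs assumed, because the documents do not give them:** the number of canals per tooth, the within-tooth ICC, and the share of adequate canals. Two of the four canal mixes examined mark the ends of the range:

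- Mix A, 60/25/10/5% of teeth with 1/2/3/4 canals: E[m] = 1.60, E[m²] = 3.30
- Mix D, 15/15/45/25%: E[m] = 2.80, E[m²] = 8.80

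**Formulas.** With m canals per tooth, the design effect is DE = 1 + (E[m²]/E[m] − 1) × ICC. The actual level of an unadjusted nominal 5% test is 2 × (1 − Φ(1.96/√DE)).

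- Mix A: DE = 1 + (3.30/1.60 − 1) × ICC = 1 + 1.0625 × ICC
- Mix D: DE = 1 + (8.80/2.80 − 1) × ICC = 1 + 2.143 × ICC

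| ICC | DE, mix A | level, mix A | DE, mix D | level, mix D |
|---|---|---|---|---|
| 0 | 1.00 | 5.0% | 1.00 | 5.0% |
| 0.1 | 1.11 | 6.2% | 1.21 | 7.5% |
| 0.4 | 1.43 | 10.1% | 1.86 | 15.0% |
| 0.7 | 1.74 | 13.8% | 2.50 | 21.5% |

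**Simulation.** Beta-binomial data were generated with no true difference, 80% of canals adequate and 20,000 trials per setting, and tested by Pearson, or by Fisher when an expected count fell below 5. Over four mixes (mean 1.60 to 2.80 canals) and 80 or 66 patients per arm, the type I error was about 5% at ICC 0, 6-8% at ICC 0.1, 10-15% at ICC 0.4 and 14-22% at ICC 0.7.

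**When inadequate canals are rare.** With 66 per arm, the test moves largely to Fisher, which is conservative:

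| Adequate canals | ICC 0.1 | ICC 0.4 | ICC 0.7 |
|---|---|---|---|
| 98% | 1.8-4.5% | 2.9-10.3% | 5.5-15.6% |
| 99% | 0.5-1.8% | 1.7-5.4% | not used here |

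**Check of the remedy.** In the 80%-adequate settings, ICC 0 to 0.7 and both sample sizes, a Rao-Scott chi-square held 4.8-5.4%, and a logistic GEE with patient as cluster held 4.6-5.4%.

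**The case against.** The strongest objection is that density may never be recorded per canal. The V1 list ties only the level of obturation to each canal; the readers' void question concerns the filling material as a whole; and the follow-up visits name no canal unit. If there is one reading per tooth, each patient contributes one observation and the planned test is valid. This stands, and it prevents a firm claim that the level will be inflated. It does not clear the plan, because 7.7.5 would then name a unit that the data do not have.

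A second objection is that details are deferred: "The statistical methods are based on the following elements and will be detailed in the Statistical Analysis Plan". But 7.7.5 already fixes both the unit and the test, so a later document that merely adds detail would carry the mismatch forward.

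A third is that clustering need not push the test above 5%. This is right: with very few inadequate canals and a low ICC, Fisher's test stays below 5%.

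A reader might also infer that confidence intervals for density would be too narrow. The plan contains none: qualitative criteria are described by counts and percentages, and the only interval specified is the one-sided 95% interval for the 2-year efficacy difference.

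**Conclusion.** Wrong as written. Section 7.7.5 pairs a canal-level unit with tests for independent observations in a trial that randomises patients, and it needs a change whichever unit is recorded.

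The size is conditional. With per-canal readings, positive within-tooth correlation, 1.6-2.8 canals per tooth on average and 80% of canals adequate, the nominal 5% becomes about 6-8%, 10-15% or 14-22% at ICC 0.1, 0.4 or 0.7. All of these inputs are assumptions. There is no inflation at ICC 0 or with one reading per tooth, and little or none when inadequate canals are very rare and the ICC is low.

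It would be tempting to read this as a threat to the trial's main conclusion. The documents do not support that: the primary non-inferiority test uses one result per patient, the sample size rests on that test, and section 7.7.8 sets no statistical stopping criterion. The point is confined to the secondary density and void comparisons.

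**What to change.** State the reading unit for density and voids in the X-ray readers' form and in the SAP, before the first central reading. Timing matters: section 7.7.9 requires the SAP only before the first interim analysis, and section 6.1 places a reading campaign ahead of each analysis.

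- **If the unit is the canal:** keep the proportion of canals as the quantity compared, and replace the planned test by a Rao-Scott chi-square or a logistic GEE with patient as cluster.
- **If the unit is the tooth:** replace canals by patients in 7.7.5 and keep the planned test.

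The cost is a change of wording and, in the first case, a standard method with somewhat less power for these secondary tests. The number of canals is already collected at V1. No new data are needed if per-canal readings exist or if the unit is the tooth; if per-canal readings are wanted but not recorded, the central reading needs a field for each canal.
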